For evaluation of response to treatment (primary endpoint), perform MRI 4-6 months after each HEC. **Except in the case of bilobar disease (for which 2 sessions of HEC should be scheduled upfront), retreatment (new HEC treatment) will be performed according to follow-up MRIs.** An MRI will be performed 4 to 6 weeks after each chemoembolization treatment. In case of tumor remnant or recurrence treatable by HEC (i.e., no portal trunk thrombosis or in a territory ≥ 3 segments, hepatopoitic portal flow, WHO status < 2 , no hepatic decompensation, no extrahepatic metastasis), a new course of HEC should be performed targeting the remnant or recurrence (same distinction as above: supra-selective OR lobar approach). In the absence of tumor remnant or recurrence on MRI performed 4-6 weeks, MRI surveillance is performed every 3 months and the modalities of retreatment are the same as before.

In all cases, MRI at 6 months from the date of inclusion must be performed (primary endpoint of the study).

At the end of the session, embolization with additional material is not recommended.

If in case of a single HEC, a recurrence of the disease is observed at the 3-month MRI, a second HEC can be performed and will be performed as part of the protocol.

V.3 Premedication and concomitant treatments

Sufficient hydration (up to 2 liters per day), adapted to the cirrhotic context, will be prescribed before and after chemoembolization for at least 48 hours.

In case of nausea or vomiting, provide adequate treatment according to center procedures.

After the procedure, level 1 to 3 (WHO) analgesics will be used in an appropriate dose.

At the end of the procedure, the pain felt by the patient will be recorded using a visual analog scale (VAS rated from 0 to 10). If VAS > 3, titration of IV morphine by an IDE according to the recommendations.

Any treatment required for patient comfort will be prescribed at the discretion of the investigator. The use of a preventive anti-emetic treatment is recommended.

VI. EXPECTED TOXICITIES AND DOSE ADJUSTMENT

VI.1 Chemoembolization

The main adverse effects expected with chemoembolization are:

- Unwanted reflux or passage of microbeads into normal arteries adjacent to the targeted lesion or through the lesion to other arteries or arterial beds
- Non-targeted embolization
- Pulmonary embolization
- Ischemia in an undesired location
- Capillary bed saturation and tissue damage
- Rupture of a vessel or lesion and hemorrhage

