- Neurological deficits including cranial nerve palsy
- Vasospasm
- Deaths
- Re-permeabilization
- Foreign body reactions requiring medical intervention
- Infection requiring medical intervention
- Catheter tip clot formation and subsequent mobilization

Expected effects related to the embolization procedure (from CNIHM anticancer files November 2008)

- Fever, hypochondrial pain, vomiting
- Transient thrombocytopenia and liver dysfunction
- Increased transaminases (cytolysis)
- Local ischemic and septic manifestations (cholecystitis, hepatic infarction, hepatic abscess, digestive hemorrhage)
- Renal insufficiency
- Hematoma at the puncture site
- Acute lower limb ischemia

Adaptation for chemoembolization

The interval between chemoembolization sessions should be 6 weeks plus or minus 1 week. Any additional time must be agreed upon by the coordinator.

HEC Session Rehearsal:

The chemoembolization session(s) are scheduled every 6 weeks, plus or minus 1 week.

The imaging technique, after each session, will be MRI and a cone beam CT acquisition (after 1^{ière} HEC for the translational study and after, if possible, each HEC to assess the quality of chemoembolization).

Subsequent sessions will be performed according to tumor response. No additional session is recommended in case of complete tumor response according to the modified RECIST criteria (mRECIST) (Appendix 2) or progression of a previously chemoembolized tumor.

In case of non-hematological toxicity of grade 3 or 4 attributable to HEC, no additional HEC is performed. In case of bleeding and/or severe liver failure and/or other toxicities secondary to a grade ≤ 3 chemoembolization session, the next session(s) will be performed at the discretion of the investigator.

Transient increases in ALT and/or AST in the 24-48 hours after HEC do not lead to failure to perform additional HEC. Indeed, this transient increase does not have a significant impact (R Sacco et al, Clinical impact of selective transarterial chemoembolization on hepatocellular carcinoma: A cohort study. World J Gastroenterol 2009 April 21; 15(15): 1843-1848).

VI.2 Idarubicin

The main effects expected for idarubicin (Zavedos® powder for solution for infusion) according to the current versions of the SPCs (version of 6/07/2006 appendix 8) are the following

- Significant spinal cord hypoplasia which can be responsible for serious or even fatal conditions
- Alopecia reversible on discontinuation of treatment

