- Digestive disorders: nausea, vomiting, diarrhea
- Stomatitis, esophagitis
- Elevated liver enzymes and bilirubin in 20-30% of cases
- Skin rash
- Acute heart rhythm disturbances, acute or late heart failure (rare before a cumulative dose of 93 mg/m²)
- Red coloration of the urine 24 to 48 hours after treatment.

As with other DNA altering anticancer agents, myelodysplastic syndromes and acute myeloid leukemias have been observed after combination therapy with anthracycline.

In case of idarubicin-related effects, no dose adjustment of idarubicin for loading the microbeads is planned. The chemoembolization session is then postponed or cancelled.

VII. MONITORING DURING AND AFTER TREATMENT

VII.1 Before each HEC

- Complete clinical examination: weight, vital signs, WHO general condition (which should be 0 or 1), pain assessment (VAS)
- Biological work-up: CBC/platelets, blood ionogram, creatinine, albumin, transaminases (AST, ALT), alkaline phosphatases (ALP), GGT, total and conjugated bilirubin, PT
- Adverse event evaluations of previous HECs according to NCI CTC version 4.0
- Quality of life questionnaires (QLQ-C30 and its module HCC18)

Prior to the session, the investigator should ensure that the patient has adequate hepatic and hematological function:

- Bilirubin ≤ 1.5 mg/dL, PNN $\geq 1,000/\text{mm}^3$, platelets $\geq 50,000/\text{mm}^3$, creatinine level $\leq 150 \mu\text{mol/L}$
- Hepatopoietic flow, thrombosis is considered significant if it involves at least 3 segments. The procedure is then contraindicated. A Doppler is strongly recommended before the embolization sessions to ensure that the procedure can be performed. It is recommended to evaluate these criteria according to the habits of the center.

For patients participating in the translational study: blood sampling for translational study (see paragraph IX)

VII.2 After each HEC

Hepatic MRI (or CT scan in case of contraindication to MRI) will be performed 4 to 6 weeks after each chemoembolization to assess their effectiveness.

Assessment imaging at 6 months from the date of inclusion MUST be performed regardless of the time of last HEC to assess the primary endpoint of the study.

Target measurements will be done according to mRECIST v1.1 to assess the primary endpoint of the study and according to EASL criteria to assess the secondary endpoint (Appendices 4 and 5).

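### Protocol VI.1, as printed, both forbids further HEC after a grade 3 non-haematological toxicity attributable to HEC and leaves it to the investigator

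*Protocol*

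**What the plan says.** Protocol VI.1, under the heading on repeating HEC sessions, has two consecutive sentences on toxicity.

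- **Stop rule:** "In case of non-hematological toxicity of grade 3 or 4 attributable to HEC, no additional HEC is performed".
- **Discretion rule:** it opens with bleeding and severe liver failure, and continues "other toxicities secondary to a grade ≤ 3 chemoembolization session, the next session(s) will be performed at the discretion of the investigator".

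One exception follows: "Transient increases in ALT and/or AST in the 24-48 hours after HEC do not lead to failure to perform additional HEC".

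Other provisions bear on whether a further session is given:

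- **Protocol V.2.3** makes retreatment of residual or recurrent tumour depend on conditions including "no hepatic decompensation, no extrahepatic metastasis". In bilobar disease the second session is not triggered by follow-up MRI; this is the case "for which 2 sessions of HEC should be scheduled upfront".
- **Protocol VI.2**, on idarubicin-related effects: "The chemoembolization session is then postponed or cancelled". No grade is given.
- **Protocol VII.1:** "Prior to the session, the investigator should ensure that the patient has adequate hepatic and hematological function", with limits for bilirubin, neutrophils, platelets and creatinine. Adverse events of earlier sessions are also reviewed.
- **Protocol VIII** stops treatment for major toxicity that requires it, without a grade.
- **Protocol XII.5** sets up an independent committee to which the sponsor may refer tolerance issues.

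SAP 4.2 allows 1 to 4 sessions per patient.

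**The concern.** The two sentences give different instructions for the same event. Suppose a patient has a grade 3 hepatic abscess attributed to the first HEC. Under the stop rule treatment ends. Under the discretion rule the investigator may go on. Two centres could act differently and each could cite the protocol.

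This is an operative safety rule for a treatment that can be repeated. The pre-session checks in VII.1 do not necessarily close the gap. VI.1 itself lists cholecystitis, hepatic infarction, hepatic abscess, digestive haemorrhage and lower limb ischaemia as expected effects of the procedure. A patient who has had one of these could meet every laboratory limit by the date of the next session.

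Uneven use of the rule would also carry into descriptive results: sessions per patient and tolerance (SAP 7.5), and time to treatment failure, in which stopping treatment is an event (Protocol XII.2.2 and SAP 7.4.3).

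**Working it through.** There is no sample-size or error-rate figure to reproduce. The check is to list which events each sentence covers.

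**Inputs (Protocol VI.1)**

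- Stop rule: non-haematological, attributable to HEC, grades {3, 4}.
- Discretion rule: bleeding, severe liver failure or any other toxicity secondary to a session, with no restriction to haematological or non-haematological, grades {1, 2, 3}. The printed word order attaches the grade to the session. Sessions have no grade, so it is read here as the grade of the toxicity.

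**Overlap for non-haematological toxicity attributable to HEC**

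{3, 4} ∩ {1, 2, 3} = {3}.

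**Coverage under three wordings of the discretion rule**

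| Toxicity | Grade | As printed (≤ 3) | Sign changed to < 3 | Wording proposed under the fix |
|---|---|---|---|---|
| Non-haematological | 1–2 | discretion | discretion | discretion |
| Non-haematological | 3 | **stop and discretion** | stop | stop |
| Non-haematological | 4 | stop | stop | stop |
| Haematological | 1–2 | discretion | discretion | discretion |
| Haematological | 3 | discretion | **neither** | discretion |
| Haematological | 4 | neither | neither | neither |

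Changing the sign removes the conflict in the second row but takes haematological grade 3 out of the only graded rule for repeat sessions. Haematological grade 4 is in neither sentence under any of the three wordings. It is left to VI.2 and the VII.1 limits, besides the ungraded stopping list in section VIII.

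**Can the two sentences be reconciled as printed?**

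- *The discretion rule is only about haematological events.* No. It names severe liver failure and adds other toxicities without limit.
- *It is only about events not due to HEC.* No. It speaks of toxicities secondary to a session.
- *It is an exception to the stop rule.* Nothing marks it as one, and its catch-all would empty the stop rule at grade 3. The exception that is intended, for transient transaminase rises, is written separately.

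**Does another section decide?** V.2.3 adds conditions but no toxicity grade. VI.2 and VIII give no grade. VII.1 sets laboratory limits, not a rule on past events. The XII.5 committee is not a per-patient retreatment rule. None ranks the two sentences.

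**Exposure for one patient.** After an event at the first session, at most 4 − 1 = 3 further sessions are at stake. On timing, "The interval between chemoembolization sessions should be 6 weeks plus or minus 1 week", so the next is due 6 − 1 = 5 to 6 + 1 = 7 weeks later.

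**The case against.** The strongest reply is that the English text is evidently a translation and the second sentence is garbled. The conflict hangs on one sign, and centres may have worked from a source text that has no such conflict. This stands as a caution and is why the source should be checked first. It does not dispose of the point. The same text prints < and ≤ or ≥ as distinct signs elsewhere (V.2.3 and VII.1), so nothing in the documents shows a slip. Nor is < an obvious intended reading: the sentence names severe liver failure, and XI.2 equates severe with grade 3 for events not on the toxicity scale.

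A second reply is that a cautious investigator would treat the explicit prohibition as governing and the next sentence as residual, where ≤ 3 still has work to do for haematological grade 3. That is a sensible reading, and the fix adopts it. The printed text does not impose it, because bleeding and liver failure are named in the residual sentence.

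A third reply is that little remains to act on. SAP 4.6.1 reports that the trial stopped for efficacy after 46 inclusions, and SAP 7.5 already reports sessions, postponements with cause, complications, toxicity by maximum grade, and serious adverse events. This lowers the importance. Bilobar disease is where the question arises most readily, since the second session is planned from the start, but the VII.1 review of adverse events and laboratory values precedes that session too.

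**Conclusion.** The conflict is real and narrow. As printed, Protocol VI.1 gives two incompatible instructions for a grade 3 non-haematological toxicity attributable to HEC, and nothing else in the documents ranks them. This rests on two assumptions: that the grade in the second sentence refers to the toxicity, and that the English text reflects the source.

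The number of patients affected cannot be estimated, because the documents give no rate of such events.

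Three stronger readings are not supported:

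- **That the rule is also contradictory at grade 4.** It is not. Grade 4 non-haematological events attributable to HEC fall under the stop alone.
- **That patients were retreated inconsistently.** The documents report no such case; they show only that the text would permit it.
- **That the primary result is in doubt.** The endpoint definition, the sample size and the decision rules do not refer to this rule and are unchanged. What is affected is patient safety, sessions per patient, tolerance and time to treatment failure.

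A reader might also infer that replacing ≤ 3 by < 3 would repair the text and leave grades 1 to 4 fully covered. It would not: haematological grade 3 would join haematological grade 4 outside both sentences.

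**What to change.** Check the source-language wording. Unless it shows otherwise, keep the stop rule as it is and reword the sentence after it, for example:

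*After any other toxicity caused by a chemoembolization session (non-haematological of grade 2 or below, bleeding and liver failure included, or haematological of grade 3 or below), the investigator decides on further sessions. Any non-haematological toxicity of grade 3 or 4 attributable to HEC, bleeding and liver failure included, falls under the preceding sentence.*

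Keep the transient ALT/AST exception and the conditions in V.2.3 and VII.1. Do not simply change the sign.

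The cost is one reworded sentence. The downside is small: some patients who have recovered from a grade 3 non-haematological event lose further sessions, which the stop rule already prescribes.

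Optionally, and not as the correction of an error, SAP 7.5 could add a short listing of any patient given a further HEC after a grade 3 or 4 non-haematological event attributable to HEC, with event, grade, dates and date of the next session. With 46 patients included it would be brief, and it would show whether the ambiguity mattered in practice.

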CAT scan for extra-hepatic evaluation	X		X (in case of contraindication to MRI)	X	X (thoracic every 6 months)	X (thoracic)
Portal Doppler if thrombosis is suspected on imaging	X	X (recommended)				
ECG	X					
Evaluation of left FEV	X					
BIOLOGICAL ASSESSMENT						
Biological check-up	X*	X**			X (liver test)	X (liver test)
AFP marker	X				X	X
Serology (HBsAg, anti-HBs, anti-HCV)	X					
Pregnancy test (within 7 days of inclusion)	X					
BIOLOGICAL STUDY						
Samples: 2 EDTA tubes of blood then centrifugation for aliquoting of 4 cryotubes of plasma and freezing at -20°C then -80°C		X (D0, D1, D2 and D3 of 1 ^{ière} HEC)				
IMAGERY*** : CT cone beam or CT scan without injection during the procedure						

* Complete biological check-up: CBC/platelets, PT, AST, ALT, alkaline phosphatases, GGT, bilirubin (total, free and conjugated), factor V, blood ionogram, creatinine, albumin, blood sugar, blood calcium

** Biological check-up before each HEC: CBC, platelets, blood ionogram, creatinine, albumin, ASAT, ALAT, PAL, GGT, total and conjugated bilirubin, PT

*** : An anonymized copy of the imaging is to be sent to the FFCD for centralized review

**** : hepatic MRI (or CT) / ultrasound of the liver by a trained operator alternating every 3 months for 2 years

I. OBJECTIVES OF THE TRIAL

I.1 Main objective

The objective of this non-randomized phase II study is to evaluate the objective response rate (complete and partial response) at 6 months, assessed according to the mRECIST criteria in centralized review.

I.2 Secondary objectives

The secondary objectives of this study are to evaluate:

- The investigator-assessed 6-month objective response rate (mRECIST)
- Time to treatment failure
- The best answer according to mRECIST
- Objective response rate at 6 months (EASL)
- Progression-free survival
- Overall survival
- Tolerance of the treatment
- Quality of life (QLQ-C30 questionnaires and its HCC18 module specific to HCC)

II. PATIENT SELECTION

II.1 Inclusion criteria

- Histologically proven HCC or according to EASL/Barcelona criteria for nodules ≥ 1 cm
- Tumor not amenable to curative treatment (liver transplantation, surgical resection or percutaneous destruction)
- Measurable targets according to mRECIST v1.1 criteria
- Preserved liver function (in case of cirrhosis, Child-Pugh A or B7 without history of edemato-ascitic decompensation)
- Tumor classified as BCLC A or B without portal or extrahepatic invasion or C if WHO= 1

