- No prior treatment with chemotherapy, radiotherapy or transarterial embolization (with or without chemotherapy)
- Age ≥ 18 years
- WHO 0 or 1
- Biological workup: platelets $\geq 50,000/\text{mm}^3$, PNN $\geq 1,000/\text{mm}^3$, creatinine level $\leq 150 \mu\text{mol/L}$
- No heart failure (isotopic or echographic LVEF $> 50\%$)
- Signed informed consent

II.2 Non-inclusion criteria

- Advanced tumor disease (vascular or extrahepatic invasion including brain metastases or diffuse HCC with $> 50\%$ liver invasion)
- History of other cancers excluding cancers known to be cured for more than 3 years (in this case histological evidence of HCC is required), or basal cell skin tumors or cervical cancer in situ adequately treated with curative intent
- Previous treatment with idarubicin and/or doxorubicin
- Contraindication to idarubicin (heart disease with myocardial insufficiency, severe renal or hepatic insufficiency, yellow fever vaccine)
- Concomitant disease or severe uncontrolled clinical situation
- Patients requiring long-term anticoagulant therapy
- Thrombosis of the portal trunk or of a territory of 3 or more segments (or hepatofugal flow of the same territories)
- Vascular involvement:

- severe atheromatous disease or,
- collateral vascular pathways potentially endangering normal territories during embolization or,
- arteritis of the hepatic artery branches to be treated, or
- arterio-port or arterio-sus-hepatic fistula not embolisable by coils
- Pregnancy or breastfeeding
- Lack of effective contraception (for men or women of childbearing age)
- Patient who for psychological, social, family or geographical reasons could not be followed regularly
- Concurrent participation of the patient in another experiment

III. PRE-INCLUSION ASSESSMENT

To be performed within 28 days prior to treatment and before inclusion:

Full clinical examination:

- Weight, height, vital signs, WHO index, pain assessment (VAS)
- Child-Pugh score if associated cirrhosis, BCLC (Barcelona Clinic Liver Cancer) score (Appendix 4)
- Medical history
- Description of the disease
- Quality of life (QLQ-C30 and its module HCC18)

Complete biological workup:

- CBC, platelets, PT, AST, ALT, PAL, GGT, bilirubin (total, free and conjugated), factor V, blood ionogram, creatinine, albumin, blood glucose, blood calcium
- Markers: α -fetoprotein (AFP)
- Serology: HBsAg, anti-HBc, anti-HCV,

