If 29 or more patients have an objective response, the treatment is declared effective (rejection of H0)

Taking into account a 5% rate of patients lost to follow-up or not evaluable, **91 patients** will be included. The decision rules will be adapted based on the number of evaluable patients actually included.

XII.4 Statistical analysis plan

A statistical analysis plan will be written prior to freezing the database.

Analysis Populations:

The characteristics of the patients included in the study will be described in strict intention-to-treat (ITT). Efficacy analyses will be performed on a modified intention-to-treat (mITT) basis: all evaluable patients included in the study regardless of eligibility criteria. A patient is considered evaluable if he/she has had at least one chemoembolization and one post-treatment evaluation.

Population evaluable for safety:

The ITT population that received at least one chemoembolization.

Statistical analysis:

The description of the variables will be done using percentages (95% confidence interval) for qualitative variables and using mean (standard deviation) and median (Min-Max) as well as the inter-quartile range (Q1-Q3) for quantitative variables.

The estimation of censored data will be done by the Kaplan Meier (KM) method. Times will be described by medians and rates at different time points with their 95% confidence intervals. The median follow-up time will be calculated using the reverse Kaplan Meir method.

XII.5 Independent Committee

An independent committee composed of 1 clinician / 1 methodologist-statistician / 1 pharmacovigilant expert / 1 radiologist will be set up before the beginning of the trial. It will meet regularly during the course of the study according to the rate of inclusion.

It will have to rule on the declared ADRs. It can also be seized at any time by the Sponsor in case of significant facts on the tolerance (ADRs and AEs) of the treatment.

XIII. JUSTIFICATION OF THE TEST

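### Bilirubin is limited before the first chemoembolization but not at entry, so an eligible patient can be registered and then left untreated and uncounted, or treated outside VII.1

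*Protocol*

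**What the plan says.** **Entry.** Protocol II.1 (and the synopsis) gives a laboratory list that opens "Biological workup: platelets" and sets limits for platelets, neutrophils (PNN) and creatinine. Bilirubin is not on it. Liver function is covered by "Preserved liver function (in case of cirrhosis, Child-Pugh A or B7 without history of edemato-ascitic decompensation". In II.2 the only other criterion on liver function is a contraindication to idarubicin, "severe renal or hepatic insufficiency, yellow fever vaccine", with no figure. Protocol III has bilirubin measured in the pre-inclusion work-up but attaches no threshold.

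**Before each session.** Protocol VII.1 states: "Prior to the session, the investigator should ensure that the patient has adequate hepatic and hematological function". The list that follows begins "Bilirubin ≤ 1.5 mg/dL, PNN" and goes on to the neutrophil, platelet and creatinine limits. Protocol IV asks that treatment start no later than 2 weeks after inclusion.

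**Analysis populations.** Protocol XII.4 defines the efficacy population: "A patient is considered evaluable if he/she has had at least one chemoembolization and one post-treatment evaluation". SAP 5.1.2 uses the same rule for the primary-endpoint (CP) population, and adds that any death in the first 6 months is evaluable and a failure. SAP 5.1.3 limits the safety population to patients with at least one chemoembolization. Both SAP sections promise a list of excluded patients with reasons.

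**The concern.** The entry rules and the first-session check do not match. Bilirubin is known before registration, yet nothing in II.1 stops a patient above the VII.1 limit from being registered. No passage says what follows if that patient then fails the check before the first session.

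There are two possible outcomes. If the patient is not treated, the evaluable definition removes the patient from the primary denominator after enrolment. The reason is linked to liver function, so it is unlikely to be unrelated to outcome. If the patient is treated, the session falls outside VII.1 although every entry criterion was met. The first outcome can raise the observed response rate and uses up the 5% allowance for non-evaluable patients. The second is a deviation that the protocol's own wording sets up.

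**Working it through.** **1. The two lists side by side**

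| Item | II.1, entry | VII.1, before each session |
|---|---|---|
| Platelets | ≥ 50,000/mm³ | ≥ 50,000/mm³ |
| Neutrophils | ≥ 1,000/mm³ | ≥ 1,000/mm³ |
| Creatinine | ≤ 150 µmol/L | ≤ 150 µmol/L |
| Bilirubin | no limit | ≤ 1.5 mg/dL |

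Three values are identical. Bilirubin is the only laboratory limit added.

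**2. Does another entry rule close the gap?** No. Child-Pugh applies only if cirrhosis is present, and SAP 7.1.3 has a no-cirrhosis category, so non-cirrhotic patients are foreseen. The exclusion for severe hepatic insufficiency has no number. This step needs no Child-Pugh scoring table.

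**3. Is the first session covered?** Yes. The VII.1 heading refers to each session. One item, adverse events of previous sessions, can apply only from the second. But VII.1 also contains "For patients participating in the translational study: blood sampling for translational study (see paragraph IX", and section IX ties that sampling to the first session.

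**4. The plan's own design, reproduced.** Inputs from Protocol XII.3: p0 = 0.25, p1 = 0.40, one-sided alpha 5%, power 90%, 43 + 43 patients, stage 1 bounds 10 and 18, final bound 29.

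- Fleming stage 1 efficacy bound: round[N·p0 + 1.645·√(N·p0(1 − p0)) − (N − n1)·p0] + 1. With N = 86 and n1 = 43: 21.5 + 6.61 − 10.75 = 17.36, so 17 + 1 = 18. Without the last term, 28.11 gives 28 + 1 = 29. Both match.
- With 44 evaluable at stage 1 (N = 87): 21.75 + 6.64 − 10.75 = 17.64, so 18 + 1 = 19, as in SAP 4.6.1.
- Exact probability of declaring efficacy, P(X1 ≥ 18) + Σ(x = 11 to 17) P(X1 = x)·P(X2 ≥ 29 − x), with X1 and X2 binomial on 43 patients: 0.0474 at p = 0.25 and 0.902 at p = 0.40.
- Inflation: 86/0.95 = 90.5, so 91, an allowance of 91 − 86 = 5 patients.

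The design figures are not in error.

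**5. The denominator.** Inputs from SAP 4.6.1: 46 included, 44 evaluable, 22 responders. Non-evaluable: 46 − 44 = 2, and 2/46 = 4.3%. The exact one-sided 95% lower bound is the 5% quantile of Beta(x, n − x + 1).

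| Denominator | Rate | Lower bound | Exact p against 25% |
|---|---|---|---|
| 44 evaluable | 22/44 = 50.0% | 36.8% | 0.0003 |
| All 46, both as failures | 22/46 = 47.8% | 35.0% | 0.0007 |

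The stage 1 bound for 46 patients, keeping 43 for stage 2 (N = 89), would be 22.25 + 6.72 − 10.75 = 18.22, so 18 + 1 = 19. The 22 responders exceed it.

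**6. How far could such losses matter in principle?** The documents give no rate, so this is an assumption shown over a range. Suppose a share e of registered patients is non-evaluable for any cause and none would have responded. A 25% rate among all registered patients is then 0.25/(1 − e) among evaluable patients, and the step 4 formula gives:

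| e | Rate among evaluable | Chance of declaring efficacy |
|---|---|---|
| 0 | 25.0% | 4.7% |
| 2% | 25.5% | 5.9% |
| 5% | 26.3% | 8.2% |
| 10% | 27.8% | 14.0% |

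These figures cover every cause of non-evaluability. The share due to the bilirubin check is unknown and may be zero.

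**The case against.** Several points on the other side are sound.

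- A reader might infer that a patient above 1.5 mg/dL is barred from treatment. The text is softer. VII.1 says what the investigator should ensure and uses the language of contraindication only for significant thrombosis. It closes by recommending that criteria be assessed by local habit, though that may refer only to portal flow. Delay and re-testing within the 2 weeks are not excluded.
- An investigator who has both sections can see the bilirubin result and decline to register the patient. A check before the procedure that is stricter than the entry limit may also be deliberate.
- A reader might infer that the affected patients lie in a bounded bilirubin range. The supplied text gives no Child-Pugh bands, and non-cirrhotic patients have no Child-Pugh ceiling, so no upper end can be stated.
- A reader might suspect a unit error, because VII.1 uses mg/dL and SAP 7.1.4 uses multiples of normal. The SAP entry is a baseline table, and nothing shows a slip.
- The evaluable definition drops untreated patients for any reason, and bilirubin is only one route. The early-death rule may keep some of them as failures. Leaving untreated patients out of a safety population is normal.
- The SAP already plans exclusion lists with reasons, and enrolment has stopped.

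These points lower the severity but leave the mismatch in place. If the VII.1 limit is advisory, or deliberately stricter than entry, the protocol does not say so. No planned analysis keeps registered but untreated patients in the denominator.

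**Conclusion.** The inconsistency is real and rests on the text alone: an entry list without a bilirubin limit, and a first-session check with one. An eligible patient can be lost from the CP and safety populations for a reason linked to liver function, or treated outside VII.1.

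A reader might go further and infer that the 2 non-evaluable patients were lost this way. The SAP gives no reasons, so 2 is a ceiling for losses by this route up to the interim analysis, and zero fits equally well. The number treated above the limit is not given either.

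With both patients counted as failures, the observed rate falls by 50.0 − 47.8 = 2.2 percentage points and the lower bound stays 10 points above 25%. The stage 1 conclusion is unchanged. The point is minor and concerns consistency and reporting, not the result.

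**What to change.** **Protocol.** Reconcile II.1 (and the synopsis) with VII.1 on bilirubin for the first session, and state what happens to a registered patient who does not meet the check. The value and the rule are the sponsor's clinical decision. This is a short text change and needs no new test, as bilirubin is already measured at screening. With enrolment stopped, it mainly clarifies the record.

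**SAP.** In 7.3.2, add one supportive estimate of the primary rate on all included patients, with untreated or non-evaluable patients as non-responders and the same exact one-sided interval. This also removes the ambiguity over an untreated patient who dies within 6 months, who is a non-responder on either reading. Use the lists already planned in 5.1.2 and 5.1.3 to identify anyone untreated because of VII.1. Those lists will not show patients treated outside VII.1; a count of these can be taken from the bilirubin recorded before each session.

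**Cost.** A few lines of text and one extra estimate. The supportive rate can only be equal to or lower than the main one unless a responder was excluded; on the interim figures it is 47.8% against 50.0%.
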